7 STATISTICAL METHODOLOGY FOR SAFETY

7.1 *Toxicity and Adverse Events*

Patients will be evaluable for safety if they have received any partial or complete treatment infusion. All AEs will be graded according to the NCI-CTCAE v.4. Treatment delays, dose reduction requirements and reason for treatment discontinuation will be monitored throughout the study.

The safety profile of patients will be monitored throughout the treatment and up to 30 days after the last treatment infusion (end of treatment, EOT), or until the patient starts a new antitumor therapy or until the date of death, whichever occurs first.

Any AEs will be coded using to the Medical Dictionary for Regulatory Activities (MedDRA). Treatment-related AEs will be followed, whenever possible, until recovery to at least grade 1 or stabilization of symptoms, whenever possible.

Summary of overall AEs will be done by body system and preferred term, by severity (worst toxicity grade) and by relationship. Tables will be sorted by body system/preferred term.

A frequency table will be made for the AEs leading to cycle delay, dose reduction, skipped dose (topotecan only), or withdrawal of study medication. AEs leading to permanent treatment stop and AEs with outcome of death will also be presented by relationship to drug.

Exploratory Fisher's exact tests will be performed to compare the incidence of grade 4 or grade 3/4 AEs between treatment arms.

7.2 *Clinical Laboratory Evaluation*

Laboratory results will be classified according to the NCI-CTCAE v.4.

The worst grade per patient will be tabulated during overall treatment and per cycle for hematology values [white blood cells (WBC), absolute neutrophil count (ANC), lymphocyte count, platelet count and hemoglobin] and for the following biochemistry tests: alanine aminotransferase (ALT), aspartate aminotransferase (AST), total bilirubin, alkaline phosphatase (AP), creatine phosphokinase (CPK), creatinine, glucose, sodium, potassium and albumin.

Exploratory Fisher's exact tests will be performed to compare the incidence of grade 4 or grade 3/4 laboratory evaluations between treatment arms.

7.3 *Physical Examination Findings*

Tables summarizing the performance status (PS), height, body weight and BSA (according to the Dubois and Dubois formula) at baseline will be prepared.

In addition, changes in the ECOG PS and body weight of each patient during the treatment compared to baseline will be presented.

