An Independent Review Committee (IRC) will determine the best patient's response and assign the date of objective response or progression/censoring according to Response Evaluation Criteria In Solid Tumors (RECIST) v.1.1. Operational details for the IRC, the algorithm and its validation by an expert panel is described in detail in the IRC charter.

An interim safety analysis will be performed in the PM01183 arm only (Arm A) when 40 patients are enrolled in this arm. Based on the results of this analysis, the IDMC may provide recommendations on the primary prophylactic use of colony stimulating factors (CSFs) as part of the therapy in the experimental Arm A. The recruitment in both treatment arms will not be stopped during the conduct of the interim safety analysis.

A futility analysis will be performed when 210 patients are recruited. The recruitment will not be put on hold. The IDMC will review efficacy and safety data available at that time and, based on the observed results, might recommend stopping the trial; no claim for efficacy in comparison with the control arm will be made at this analysis.

Crossover after treatment discontinuation from the control Arm B to the experimental Arm A is not allowed.

A summary of the study design is shown in the below figure.

*If the patient had not previously received PLD or topotecan, the assigned treatment in case that the patient is randomized to the control arm (Arm B) will be based on the reported Investigator's preference with regard to each one of these two drugs. However, if the number of patients randomized to either PLD or topotecan reaches the 60% of the total number of patients expected in the control arm (i.e., 126 patients), then the treatment of choice in the control arm will be restricted to the less frequent control drug until the end of accrual.

Patients will receive the study treatment while it is considered to be in their best interest. Specifically, treatment will continue until disease progression, unacceptable toxicity, intercurrent illness of sufficient magnitude to preclude safe continuation of the study, Investigator's decision, patient refusal, non-compliance with the study requirements, a major protocol deviation that may affect the risk/benefit ratio for the participating patient, or requirement of > two dose reductions.

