5.2 Sample Size

This phase III clinical trial is designed to determine a statistically significant difference in PFS by IRC between PM01183 and a control arm with PLD or topotecan in ovarian cancer patients with platinum-resistant disease.

Patients will be randomized to receive PM01183 given as 3.2 mg/m² (Arm A) or either topotecan or PLD (Arm B).

The prospective assumptions are a 30% reduction in the relative risk of progression or death (HR=0.7) to be achieved with the experimental arm (PM01183), at a one-sided 2.5% significance level with at least 90% power, following exponential distributions and fulfilling the proportional hazard assumption. Median PFS with control arm is expected to be around 3.5 months. It is forecasted that an observed HR of approximately 0.8 will have enough power to reject the null hypothesis (HR=1).

Approximately 420 patients with platinum resistant ovarian cancer will be necessary to stratify and randomize at a 1:1 ratio over 18 months (~23 patients/month). The required 332 PFS events are expected to occur around six months after randomization of the last patient. Therefore, the IDMC meeting after the IRC review to test PFS is expected to occur about one year after randomization of the last patient.

With the prospective assumptions above mentioned, about 175 PFS events are expected in the control arm and 157 in the PM01183 treatment arm.

The IDMC will review the results of the analyses. The IRC will determine the patient's best response and assign the date of objective response or progression/censoring according to the RECIST v.1.1.

5.2.1 *Futility Analysis*

A futility analysis will be performed when 210 patients are recruited (i.e., ~105 patients enrolled in each arm). The recruitment will not be put on hold.

In the futility analysis, the sponsor will make no claim of efficacy, consequently this futility analysis and the final analysis to reject the null hypothesis ($HR=1$) are planned; the significance level will be determined by the actual number of observed events by IR. To maintain scientific integrity, type II error will be controlled by a spending function defined by O'Brien-Fleming boundaries. Following the prospective assumptions, the interim analysis will occur at less than one year after start of recruitment. At this moment, with the available information collected after balancing efficacy and safety, the IDMC might recommend stopping the trial.

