8.3 Treatment Administration

Total cumulative dose, time on treatment, dose intensity and relative dose intensity, administration delay, and dose reductions/omissions will be described following standard tables (detailed in Appendix I) and the reported cycle information on the case report form (CRF) pages will be used for the analyses.

Total cumulative dose by drug, expressed in mg, is the sum of all the product doses from the first cycle until the last cycle, including the dose received in the last cycle.

Time on treatment, expressed in weeks, is defined as last infusion date minus first infusion date plus 30 days, except if the patient dies or starts a new antitumor therapy within 30 days from the last infusion date, in which case the time on treatment will be the date of death or the date of the start of a new antitumor therapy minus the date of the first infusion.

Intended dose intensity is the planned dose per cycle divided by the planned number of weeks by cycle.

Absolute dose intensity is the actual cumulative dose divided by the number of weeks of treatment. As a convention, for this calculation, the duration of the last cycle will be the predefined cycle length (i.e., 21 days or 28 days in case of PLD). Relative dose intensity (%) is the ratio of absolute dose intensity divided by the intended dose intensity.

The items « Infusion delayed: yes/no» and « Dose reduced: yes/no» present on the drug

administration CRF page will be used to calculate delays and dose reductions, respectively. For cycles considered as delayed by the Investigator, the length of the delay will be calculated as:

Duration of cycle delay: Date of the current drug administration – Date of the previous drug administration – the predefined cycle length (i.e., 21 days if PM01183/topotecan or 28 days if PLD).

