	No. of patients evaluated	Grade 3/4	%	No. of patients evaluated	Grade 3/4	%	No. of patients evaluated	Grade 3/4	%
PM01183									
Thrombocytopenia									
Neutropenia									
ALKP									
Bilirubin									
SGOT-AST									
SGPT-ALT									
CPK									
Nausea									
Vomiting									
Fatigue									
Other*									
Control									
Thrombocytopenia									
Neutropenia									
ALKP									
Bilirubin									
SGOT-AST									
SGPT-ALT									
CPK									
Nausea									
Vomiting									
Fatigue									
Other*									

*Any drug-related toxicity present in $\geq 3\%$ of cycles in any group.

Table 12.5.9 Worst grade by patient comparison vs. PLD

Laboratory abnormalities/ drug-related AEs	Grade																			
	PM01183										PLD									
	0		1		...		G≥1		G≥3		0		1		...		G≥1		G≥3	
	N	%	N	%	N	%	N	%	N	%	N	%	N	%	N	%	N	%	N	%
Thrombocytopenia																				
Neutropenia																				
ALKP																				
Bilirubin																				
SGOT-AST																				
SGPT-ALT																				
CPK																				
Nausea																				
Vomiting																				
Fatigue																				
Other*																				

*Any drug-related toxicity present in >=5% of patients in any group.

Table 12.5.10 Worst grade by cycle comparison vs. PLD

Laboratory abnormalities/ drug-related AEs	Grade																			
	PM01183										PLD									
	0		1		...		G≥1		G≥3		0		1		...		G≥1		G≥3	
	N	%	N	%	N	%	N	%	N	%	N	%	N	%	N	%	N	%	N	%
Thrombocytopenia																				
Neutropenia																				
ALKP																				
Bilirubin																				
SGOT-AST																				
SGPT-ALT																				
CPK																				
Nausea																				
Vomiting																				
Fatigue																				
Other*																				

*Any drug-related toxicity present in >=5% of patients in any group.

Table 12.5.11 Worst grade by patient comparison vs. topotecan

Laboratory abnormalities/ drug-related AEs	Grade																			
	PM01183										Topotecan									
	0		1		...		G≥1		G≥3		0		1		...		G≥1		G≥3	
	N	%	N	%	N	%	N	%	N	%	N	%	N	%	N	%	N	%	N	%
Thrombocytopenia																				
Neutropenia																				
ALKP																				
Bilirubin																				
SGOT-AST																				
SGPT-ALT																				
CPK																				
Nausea																				
Vomiting																				
Fatigue																				
Other*																				

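### Arms are compared on adverse events only by crude per-patient incidence, although the design implies a longer observation window in Arm A; add a time-to-first-event comparison and exposure-adjusted rates beside it

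*SAP*

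**What the plan says.** SAP 7.1 states that Fisher's "exact tests will be performed to compare the incidence of grade 4 or grade 3/4 AEs between treatment arms". The sentence opens by labelling these tests exploratory. SAP 7.2 plans the same for laboratory abnormalities. Tables 12.4.4.10 and 12.4.4.11 classify each patient by worst grade, split at grade 3 and at grade 4, for ten named terms plus any drug-related toxicity seen in at least 5% of patients in either group.

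Under SAP section 2, "treatment will continue until disease progression", or until one of several other reasons such as toxicity, refusal or investigator's decision. AEs are monitored on treatment and up to 30 days after the last infusion, ending earlier at death or new antitumor therapy (SAP 7.1). SAP 8.3 already derives the matching exposure variable: "Time on treatment, expressed in weeks, is defined as last infusion date minus first infusion date plus 30 days", with the same two exceptions. It is summarised by drug in Table 12.1.1.1 but is not used as an AE denominator.

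On efficacy, SAP 5.2 says "Median PFS with control arm is expected to be around 3.5 months", with a hazard ratio of 0.70, "following exponential distributions and fulfilling the proportional hazard assumption".

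The other safety displays are descriptive. They include AEs by worst grade per cycle, first-cycle laboratory shifts, and by-cycle comparisons with each control drug, such as "Table 12.5.10 Worst grade by cycle comparison vs. PLD". Neither document plans an exposure-adjusted rate, a time-to-first-event safety analysis or a test restricted to a common time window.

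**The concern.** The share of patients with at least one event rises with the time they are watched. If PM01183 delays progression as the design assumes, Arm A patients will on average be treated and observed longer. An AE with the same monthly risk in both arms will then appear in more Arm A patients, and part of the drug's longer benefit would read as extra toxicity. If PM01183 patients instead stop earlier, the same comparison would understate a real excess. The affected p-values repeat over many rows, and they are the only formal between-arm AE comparison in the report.

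**Working it through.** **Inputs from the documents.** Hazard ratio 0.70, control median PFS 3.5 months, exponential times, 332 events, 420 patients at 1:1 (SAP 5.2); AE window of treatment plus up to 30 days (SAP 7.1); cycles of 21 days for PM01183 and topotecan and 28 days for PLD (SAP 8.3).

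**Assumptions not in the documents.** Fisher test at two-sided 0.05; 210 treated patients per arm; one constant monthly AE hazard λ, equal in both arms; a full 30-day tail; the share of patients who stop for reasons other than progression.

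**1. The plan's own figure.** Schoenfeld's formula gives 4 × (1.960 + 1.282)² / (ln 0.70)² ≈ 331 events, against the stated 332. The critical observed hazard ratio is exp(−1.960 × 2/√332) = 0.806, matching the stated value of about 0.8. The design inputs are therefore read correctly.

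**2. Length of the AE window.** The Arm A median is 3.5/0.70 = 5.0 months. Progression hazards are ln 2/3.5 = 0.198 (control) and ln 2/5.0 = 0.139 (Arm A) per month, so mean times to progression are 5.05 and 7.21 months, a ratio of 1.43. Adding 30/30.44 = 0.99 month to each gives 6.04 and 8.20 months, a ratio of 1.36. Now let a fraction f of control patients stop for other reasons, with the same extra hazard 0.198 × f/(1 − f) in both arms. The ratio falls to 1.30 (f = 10%), 1.25 (20%) or 1.21 (30%).

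**3. Crude incidence at equal monthly risk.** With progression hazard μ, incidence = 1 − exp(−0.99λ) × μ/(μ + λ). For λ = 0.040:
- control: 1 − 0.961 × 0.198/0.238 = 20.0%
- Arm A: 1 − 0.961 × 0.139/0.179 = 25.4%

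The chance that Fisher's test rejects with PM01183 worse was summed exactly over all 2×2 tables:

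| Control incidence | Arm A incidence | PM01183 shown as worse |
|---|---|---|
| 5% | 6.7% | 7.6% |
| 10% | 13.1% | 13.5% |
| 20% | 25.4% | 22.5% |
| 40% | 47.6% | 31.8% |
| 60% | 67.2% | 29.6% |
| 80% | 84.6% | 19.6% |

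With equal exposure the same test does this 1.5% to 2.1% of the time. With 10% to 30% of control patients stopping for other reasons, and control incidences of 20% to 60%, the figure lies between 25% and 10%.

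**4. Early toxicity.** If all AE risk falls in the first one to three months, the figure is 1.9% to 4.2%, close to the equal-exposure value.

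**5. By-cycle tables.** Risk per cycle is 1 − exp(−λ × days/30.44). At λ = 0.05 this is 3.4% for a 21-day cycle and 4.5% for a 28-day cycle. At equal daily risk PLD therefore looks about one third worse per cycle. Topotecan has the same nominal 21-day cycle as PM01183, so that comparison is roughly fair.

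**6. Does an events-per-month rate repair it?** Under a constant hazard, yes: in 20,000 simulated trials per scenario, the log rate-ratio test wrongly shows PM01183 as worse 2.1% to 2.6% of the time. Under early risk, no. With an identical hazard of 0.1 to 0.3 per month in months 0 to 2 and none afterwards, crude incidences are nearly equal (17.5% against 17.3% at the low end, 43.9% against 43.4% at the high end). The rate ratio is nevertheless about 0.75 to 0.77, and it falsely calls PM01183 less toxic in about 26% to 45% of trials. Arm A's later, event-free months inflate its denominator. A time-to-first-event comparison avoids both errors, because it compares patients still at risk at the same time since first infusion.

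**The case against.** The strongest reply is that a constant hazard fits these toxicities poorly. In the first-in-human study the neutrophil nadir usually fell in the second week, and no drug accumulation was found (protocol 1.2.1.3). Day 8 laboratory tests are scheduled only in Cycles 1 and 2 (protocol 5.7). Severe toxicity leads to secondary CSF or dose reduction (protocol 6.6), which should lower later risk. Seven of the ten named rows in Tables 12.4.4.10 and 12.4.4.11 are laboratory parameters. This largely stands for neutropenia. It is weaker for events that build up over treatment.

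The tests are also labelled exploratory, no decision rule depends on them, and time on treatment is reported alongside. That stands too, and it limits the point to a supplementary analysis.

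A reader might infer three stronger things that the documents do not support:
- **That the trial assumes 43% longer treatment.** The 43% is 1/0.70, the assumed gain in PFS. No treatment duration is assumed, patients stop for other reasons too, and the 30-day tail in both arms narrows the ratio.
- **That no planned display gives risk on a comparable time scale.** The by-cycle tables against topotecan come close; the mismatch is with PLD.
- **That the rate per patient-month should replace the crude comparison.** Step 6 shows that it would introduce the opposite bias for early toxicity.

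**Conclusion.** The point holds as a modest gap in the safety analysis. The only between-arm tests use crude incidence, and the plan has no comparison that accounts for time at risk. For events accruing at a constant and equal monthly risk, the false signal against PM01183 is roughly 8% to 32% per AE term, against about 2% with equal exposure. It is never a majority of trials, it is below 15% for events with control incidence of 10% or less, and it nearly vanishes for early-onset toxicity. The size rests on the design hazard ratio being true, treatment to progression with a full 30-day tail, 210 treated patients per arm and a two-sided 0.05 level. More non-progression stops shrink it. If the hazard ratio is nearer 1, the bias shrinks with it. The primary analysis is unaffected.

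**What to change.** In SAP 7.1 and 7.2, for the grade 3/4 and grade 4 terms in Tables 12.4.4.10 and 12.4.4.11, add:

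1. A time-to-first-event comparison: Kaplan-Meier cumulative incidence by arm and a Cox hazard ratio with 95% CI, censored at the end of the SAP 8.3 on-treatment period.
2. Exposure-adjusted rates: first events per patient-month at risk.

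Keep the crude percentages and exploratory Fisher tests beside them. State that the patient-month rate ratio is not the sole basis for between-arm statements, and that it assumes a roughly constant hazard. Add a note to the by-cycle tables against PLD that the cycles are 28 and 21 days.

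The cost is a few table columns and some programming. AE start dates and the SAP 8.3 exposure variable already exist, so no new data are needed. One limitation should be stated: stopping treatment is treated as uninformative censoring, which is doubtful when patients stop because of toxicity. This is a further reason to keep the crude figures in view.

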7.4 Deaths and other Serious Adverse Events

Deaths, and other serious adverse events will be tabulated following the same pattern than AEs.

8 OTHER ANALYSES

Non-continuous variables will be described in frequency tables using counts and percentages. Continuous variables will be described by median, mean, standard deviation (STD), minimum and maximum.

8.1 Baseline and Demographic Data

Baseline data such as demographics, cancer history, number of organs involved and sites of disease, prior therapy, laboratory values at baseline, prior relevant history, signs and symptoms, electrocardiogram, and concomitant medication [Anatomical Therapeutic Chemical – World Health Organization (ATC-WHO) coded] will be described following standard tables (detailed in Appendix I) for all randomized patients.

For pre-treatment characteristics with multiple measurements per patient before the start of treatment (e.g. laboratory assessments, vital signs), the baseline measurement will be considered the last value prior to or on the first day of treatment for tabulation and analysis. However all the baseline assessments will be listed (see section 13).

